## Study Summary

Title	Use of continuous glucose monitoring system with intensive feedback in adolescents with poorly controlled type 1 diabetes
Short Title	Use of continuous glucose monitoring system with intensive feedback in adolescents with poorly controlled type 1 diabetes
Protocol Number	16-01011
NCT Number	NCT03020069
Principal Investigator	[name]
Methodology	Randomized open label
Study Duration	Estimated duration for the main protocol (e.g. from start of screening to last subject processed and finishing the study)
Study Center(s)	Single-center or multi-center. If multi-center, note number of projected centers to be involved.
Objectives	to determine if using a glucose sensor helps adolescents with t1D understand their range of options in controlling their diabetes
Number of Subjects	60
Diagnosis and Main Inclusion Criteria	Adolescents with type 1 diabetes and an HbA1c $\geq 8\%$

CONFIDENTIAL

This material is the property of the NYU School of Medicine and Langone Medical Center. Do not disclose or use except as authorized in writing by the study sponsor

## Use of continuous glucose monitoring system with intensive feedback in adolescents with poorly controlled type 1 diabetes

Version Date: 04/26/2018

Type 1 diabetes (T1D) is one of the most common chronic diseases presenting in childhood. The prevalence ranges from 1 case per 1430 children at 5 years of age to 1 case in 360 at 16 years of age worldwide in the last few years. The incidence of T1DM has increased by about 2-3 % each year. Management of T1D requires frequent blood glucose monitoring, insulin injections and careful attention to diet. Hemoglobin A1c is a measure of average blood glucose over the prior 60-90 days. The 2014 ADA goal for target HbA1c in adolescents is below 7.5 % but this is seldom achieved. There are multiple challenges to managing T1D in adolescents. The insulin requirements are constantly changing as adolescents go through puberty, lead more independent lives and make their own food choices. In addition, adolescents may not feel the need to work hard to control their diabetes as they feel healthy and have a sense of invulnerability and immortality. Tight blood glucose control requires frequent changes in the insulin regimen and pattern recognition. Even when patients check blood glucose levels regularly, it is measured only 4-8 times per day while fluctuations in blood glucose occur continuously. Introduction of continuous glucose monitoring (CGM) provides a measure of blood glucose level every 5 minutes. CGM is FDA approved for use in children as an adjunct to but not a replacement for capillary blood glucose testing. In the Type 1D exchange clinic registry {Wong, 2014 #75}, 9 % of over 17,000 participants used CGM (6% of children <13 years old, 4% of adolescents 13 to <18 years, 6% of young adults 18 to <26 years, and 21% of adults ≥26 years). On July 21, an FDA advisory panel voted 8-2 to allow patients to use Dexcom's G5 CGM data for making treatment decisions without a finger stick verification. Society representative [name] testified in support of the label change citing the device's safety and the need for additional guidance on how to use unverified CGM data effectively. The panel's recommendation will now be considered by the FDA which, if accepted, will carve a path forward for Medicare coverage of the device. Currently CGM is not universally covered by private insurance. This wealth of information could theoretically allow adolescents to understand their diabetes better as well as help the physician in making changes in insulin regimen while avoiding hypoglycemia. Studies in adults have shown CGM significantly lowers HbA1c levels without increasing risk for hypoglycemia. However research has shown that HbA1c did not improve in adolescents with T1D placed on CGM (presumably due to the lack of consistent use) but HbA1c was lowered in young children and adults on CGM. While development of a closed loop system for diabetes management will require CGM, adolescents are often resistant to wearing the CGM device.

### AIM:

To determine if short-term use of continuous glucose monitoring systems (CGMS) with intensive real time feedback about diabetes management from medical staff to the patient will affect motivation and/or behavior, in adolescents with poorly controlled type 1

CONFIDENTIAL

This material is the property of the NYU School of Medicine and Langone Medical Center. Do not disclose or use except as authorized in writing by the study sponsor

Use of continuous glucose monitoring system with intensive feedback in adolescents with poorly controlled type 1 diabetes  
Version Date: 04/26/2018

diabetes. Previous CGMS studies have tended to focus on participants who are in better glycemic control at baseline and who report better adherence and diabetes-related quality of life than expected of a randomly selected sample of subjects with type 1 diabetes.

Studying a more broadly representative group that includes subjects with poor glycemic control will provide helpful information about glycemic and psychological effects of CGMS in an at risk group(1). Research indicates that various psychological skills and psychosocial factors, including coping and social support play a large role in the efficacy of CGMS use(2).

We hypothesize that short-term CGMS use with feedback (and/or lack thereof) and patients' sense of self-efficacy will influence their stage of change and potentially glucose levels.

#### SUBJECTS:

Sixty adolescents, ages 13-22 years, with type 1 diabetes and an HbA1c  $\geq 8\%$  who are also naive to CGMS or who have not used a CGMS in at least six months use will be recruited from the diabetes outpatient population followed at Bellevue Hospital, Lutheran Hospital, Woodhull Hospital, and the NYU Fink Pediatric Ambulatory Care Center. Forty subjects will be randomly assigned to the CGMS group and 20 subjects will be assigned to the control group.

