#### Screening procedures to determine eligibility:

At the medical appointment for each patient to determine eligibility for the study the research personnel will verify age, diagnosis of t1D, and HbA1c from data in the electronic medical record, investigator will also determine if the potential subject has any exclusion criteria listed below.

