#### Exclusion Criteria:

Patients with developmental delay, and patients who do not use a glucose meter to test capillary blood glucose level, and patients without access to a telephone will be excluded.

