#### ANALYSIS:

Measures of the level of glycemic control will be assessed primarily by HbA1c and secondarily by the average glucose tests results on the patient's glucose meter. Comparison of the glucose results (average, range, standard deviation, number of daily tests) between the study entry, 1 week, 1 month and 3 month follow up visits will be done. Comparison of HbA1c at entry and at 3-month follow-up will be performed. Questionnaire scores will be compared between study entry, 1 week follow up, 1 month follow up and 3-month follow-up visits for DES and Stages of Change scales. We will determine if there is a correlation between the scores on the questionnaires and measures of glucose control. We will classify study and control participants into adherent and non-adherent groups.

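### Eligibility sets no minimum time since diagnosis, so a few patients may qualify on an HbA1c that partly predates treatment, and its later fall would count as 3-month change

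*Combined protocol and SAP*

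**What the plan says.** **Inclusion.** SUBJECTS opens with "Sixty adolescents, ages 13-22 years, with type 1 diabetes and an HbA1c" of at least 8% and adds "who are also naive to CGMS or who have not used a CGMS in at least six months". Patients are to be "recruited from the diabetes outpatient population followed at Bellevue Hospital" and three other sites. Forty are randomised to CGMS and 20 to control; no stratification is described.

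**Exclusion.** Exclusion Criteria begins "Patients with developmental delay, and patients who do not use a glucose meter to test capillary blood glucose level" and adds patients without a telephone. Recent diagnosis is not listed.

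**Screening.** Under Screening procedures to determine eligibility, "the research personnel will verify age, diagnosis of t1D, and HbA1c from data in the electronic medical record", and the investigator also checks the listed exclusions. The date of diagnosis is not among the items, and no limit is set on the age of the recorded HbA1c.

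**What HbA1c measures.** The background section states: "Hemoglobin A1c is a measure of average blood glucose over the prior 60-90 days".

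**Analysis.** ANALYSIS makes HbA1c the primary measure of glycaemic control and says: "Comparison of HbA1c at entry and at 3-month follow-up will be performed". Statistical methods classes each change, with a fall of 0.5 or more counted as Lower. No between-arm HbA1c test is stated, and nothing is adjusted or stratified by duration of diabetes.

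**The concern.** The AIM section concerns motivation and behaviour in adolescents whose diabetes is poorly controlled. The only working definition of poor control is HbA1c of at least 8%. That threshold cannot separate a patient who has managed the disease for years with poor results from one whose HbA1c is high because treatment began a few weeks ago.

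For the second patient the two HbA1c values measure different things. The entry value looks back partly over untreated time. The 3-month value, with the same 60-90 day window, does not. Some fall is then expected whether or not a sensor was worn.

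The plan as written describes comparisons across visits, so nothing in it subtracts the control arm's change from the CGMS arm's. The fall would be read as change, and where it reaches 0.5 the patient would be counted as Lower.

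**Working it through.** The documents give no power, effect size, SD or dropout for the 60 subjects, so there is no stated figure to reproduce beyond 40 + 20 = 60.

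**1. Is the gap there?** Inclusion covers age, diagnosis, HbA1c and CGMS use. Exclusion covers developmental delay, no meter use and no telephone. Screening covers age, diagnosis, HbA1c and those exclusions. No section mentions time since diagnosis or time on insulin. A CGMS-naive outpatient four weeks after diagnosis, with a meter, a telephone and HbA1c above 8%, is eligible.

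**2. How many such patients?** The documents give no count. The background section gives prevalence of 1 in 1430 at age 5 and 1 in 360 at age 16. Assume cases accumulate evenly over those 11 years.
- New cases per year: (1/360 - 1/1430)/11 = 0.00019.
- As a share of prevalent cases at 16: 0.00019/(1/360) = 6.8% a year.
- Within 90 days: 6.8% x 90/365 = 1.7%, or 60 x 0.017 = about 1 patient.
- If every recent case but only half of established patients reach 8%: 0.0168/(0.0168 + 0.5 x 0.9832) = 3.3%, or about 2 of 60.

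This is rough. Incidence may be higher around puberty, and new patients may attend more often.

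**3. Shift in the pooled entry-to-3-month mean.** Shift = (k/60) x d, where k is the number of such patients and d is their extra fall in HbA1c points. The value of d is an assumption.
- k = 1, d = 3: 0.05.
- k = 2, d = 3: 0.10.
- Wider range, k = 3, d = 2: 0.10; k = 6, d = 4: 0.40.

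**4. Spread and precision.** Assume an SD of change of 1.0 in the other patients and let f = k/60. Then total SD = sqrt(1 + f(1 - f)d²). Columns five and six use normal approximations at two-sided 0.05: the chance of a significant fall in the 40 CGMS patients with no device effect is Φ(shift/(SD/√40) - 1.96), and power for a 0.5-point arm difference is Φ(0.5/(SD x √(1/20 + 1/40)) - 1.96).

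| k | d | Shift | SD | Chance of spurious fall | Power |
|---|---|---|---|---|---|
| 0 | - | 0 | 1.00 | 2.5% | 45% |
| 1 | 3 | 0.05 | 1.07 | 5% | 40% |
| 2 | 3 | 0.10 | 1.14 | 8% | 36% |
| 3 | 2 | 0.10 | 1.09 | 8% | 39% |
| 6 | 3 | 0.30 | 1.35 | 29% | 27% |
| 6 | 4 | 0.40 | 1.56 | 37% | 21% |

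The plan names no test for HbA1c, so the last two columns are illustrations of what a before-after or a between-arm test would do.

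**5. Between arms.** If x of the k patients fall in the CGMS arm, the difference in share is x/40 - (k - x)/20 = 0.075x - k/20. Its mean under randomisation is 0. Its SD is 0.075 x sqrt(k x (2/9) x (60 - k)/59), which is multiplied by d to give HbA1c points. With d = 3:
- k = 1: SD 0.11 points.
- k = 2: SD 0.15 points.
- k = 6: SD 0.25 points, with a 17% chance of a shift of 0.3 or more in either direction.

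**The case against.** The case for leaving the criteria alone has four parts, and much of it stands.

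**Few patients are affected.** Recruits are outpatients already followed, approached at regularly scheduled appointments, who use a meter and have a current self-management plan. This stands. It makes the number small without making it zero, and it is why 1-2 of 60 is a better working figure than 3-6.

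**The fall is not the same for everyone within 90 days.** By the protocol's own window, a patient enrolled at day 60-80 has an entry HbA1c that mostly reflects treated time, so only very early enrolments approach the full assumed fall. This stands too; applying 3 points to every such patient leans towards overstating the shift.

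**Randomisation deals with it.** It does so for a between-arm contrast, where the expected bias is zero. But the plan states no such contrast for HbA1c. Adding one would remove most of the harm; the extra noise would remain.

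**The trial wants breadth.** AIM seeks a more broadly representative group. That is set against earlier studies of better-controlled participants, and it gives no reason to admit values that predate treatment.

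A reader might also infer stronger points that the documents do not support:
- *That the CGMS-naive criterion selects recent diagnoses.* The background section puts CGM use at 4% of those 13 to under 18 and 6% of those 18 to under 26, so nearly everyone meets the criterion whatever their duration, and lapsed users are admitted as well.
- *That screening checks nothing beyond age, diagnosis and HbA1c.* The same sentence goes on to the exclusion criteria. Duration is still absent.
- *That three such patients, all in the control arm, would move its mean by 3/20 x 3 = 0.45, close to the plan's 0.5.* The probability of that allocation is C(20,3)/C(60,3) = 1140/34220 = 3.3%, and 0.5 classifies an individual's change. It is not a margin for arm means.

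**Conclusion.** The omission is real and its likely effect is modest. A patient within about 90 days of diagnosis can qualify, and the resulting fall would be read as change in the comparisons the plan describes. On the rough estimate of 1-2 such patients and an assumed 3-point fall, the pooled mean change moves by about 0.05-0.10 points; 3-6 patients with a 2-4 point fall would move it by 0.10-0.40. Between arms there is no expected bias, only noise and chance imbalance.

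These sizes rest on even accrual of cases between ages 5 and 16, the assumed share of established patients at or above 8%, the assumed fall and, for precision, an assumed SD of change of 1.0. None of the last three is in the documents. The case for acting is that the correction is cheap, since the likely distortion is small.

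**What to change.** Add to SUBJECTS, and to the screening check, that both the qualifying HbA1c and the entry HbA1c must be drawn more than 90 days after the diagnosis of type 1 diabetes. Ninety days is the upper end of the window the protocol gives for HbA1c; the investigators may prefer a longer minimum.

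If patients inside that window are already enrolled, keep them in the main analysis and repeat the HbA1c and meter-glucose analyses without them, reporting both. This needs the date of diagnosis for every participant. The demographic form is not included in the text reviewed, so it may already be collected.

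The cost is one eligibility line and one date from a medical record that screening already opens. The downside is that a few recently diagnosed patients are deferred or excluded, which slows recruitment slightly.

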#### Screening procedures to determine eligibility:

At the medical appointment for each patient to determine eligibility for the study the research personnel will verify age, diagnosis of t1D, and HbA1c from data in the electronic medical record, investigator will also determine if the potential subject has any exclusion criteria listed below.

#### Exclusion Criteria:

Patients with developmental delay, and patients who do not use a glucose meter to test capillary blood glucose level, and patients without access to a telephone will be excluded.

#### METHODS:

Throughout the study, all communication with the subject and his/her parent will be conducted in the preferred language of the patient and in that of his/her parent. If required, an interpreter will be utilized by telephone.

An introduction to the relationship between HbA1c, average blood glucose, and the complications of chronically elevated blood sugar levels will be provided during recruitment. Potential subjects will be identified at their regularly scheduled clinic

#### CONFIDENTIAL

This material is the property of the NYU School of Medicine and Langone Medical Center. Do not disclose or use except as authorized in writing by the study sponsor

Use of continuous glucose monitoring system with intensive feedback in adolescents with poorly controlled type 1 diabetes  
Version Date: 04/26/2018

appointments and staff will determine if they are interested in participation in the study using a recruitment script uploaded under recruitment materials section.

The study is minimal risk (MR). The device is approved by the FDA and is being used according to its cleared/approved labeling. The probability and magnitude of harm or discomfort anticipated in this research is similar to those ordinarily encountered in daily life or during the performance of routine physical or psychological examinations or tests.

The use of the CGMS will be described.

The study will consist of 4 phases.

1: For all participants at entry into the study the participant's HbA1c will be measured in the lab at the location of the patient's visit and his/her glucose meter will be downloaded as part of routine care. The average capillary glucose level, (with range and standard deviation) and the average number of tests per day over the prior 14 days will be recorded. The current individual care plans for self-management of type 1 diabetes will be reviewed by the study personnel with the participant.

Questionnaires will be administered to all the participants except Appendix F:

- 1) Appendix A - Stages of Change measure (original). We created a 5 item questionnaire to assess the patient's current stage.
- 2) Appendix B - Psychosocial self-efficacy (University of Michigan Diabetes Research and Training Diabetes Empowerment Scale short-form) - DES. 8 items. Also available for use.(3-6)
- 3) Appendix C - Knowledge and risk perception (University of Michigan Diabetes Research Training Center Diabetes Knowledge Scale). 23 items - DKT. We are substituting rapid acting insulin for NPH insulin in item 17 since NPH is not used in our study population. Available for use without permission as long as the source is quoted.(7, 8)
- 4) Appendix D - Quality of life (Peds QL 3.2, Diabetes module,) – Peds QL. 33 items on a Likert scale.(9)
- 5) Appendix E - Depression (PHQ-2.). 2 items. If the patient receives a score of 3 or above, a referral to psychiatric services will be made. No permission required to reproduce, translate, display or distribute.(10, 11)
- 6) Appendix F – CGM Satisfaction Scale. To be administered at second visit. See below number 2 on protocol. Will only be administered to study group.
- 7) Appendix G - Demographic variables will be collected.
- 8) Appendix H - Telephone administered questionnaire.
9. Appendix I – data to be tabulated in research database in RedCap

---

[figure not shown]
CONFIDENTIAL

This material is the property of the NYU School of Medicine and Langone Medical Center. Do not disclose or use except as authorized in writing by the study sponsor

Use of continuous glucose monitoring system with intensive feedback in adolescents with poorly controlled type 1 diabetes  
 Version Date: 04/26/2018

Standard scoring will be used for the DKT, DES, PHQ-2 and Peds QL.  
 Standard scoring instructions will be followed for published tests.  
 The CGMS will be used only in the study group. The CGMS that will be used will be Dex-COM® which consists of the sensor, transmitter and the receiver. The Dex-COM CGM device is FDA approved for use in patients 2 years and older.

**Sensor** - The sensor is packaged in a sterile sealed pouch, containing an applicator, sensor pod and sensor wire. The applicator barrel helps to insert the sensor wire inside the sensor pod under the skin. After inserting the sensor wire, the applicator barrel is removed. The sensor wire stays in the sensor pod with the pod attached to the skin by adhesive. The sensor wire is made of silver and platinum with polymer membranes. Once inserted, the thin and flexible wire measures the glucose levels in the fluid between the cells (interstitial fluid) for up to seven days. Dexcom sensor is inserted in the belly/abdomen (ages 2 years and older) or the upper buttocks (ages 2 to 17 years). The sensor is water resistant

**Transmitter** - Snapping into the sensor pod, the gray plastic transmitter wirelessly sends your glucose information to your display devices—receiver. The transmitter is re-usable and water-resistant.

CONFIDENTIAL

This material is the property of the NYU School of Medicine and Langone Medical Center. Do not disclose or use except as authorized in writing by the study sponsor

Use of continuous glucose monitoring system with intensive feedback in adolescents with poorly controlled type 1 diabetes  
Version Date: 04/26/2018

**Receiver** - The receiver is a small hand-held device. The receiver shows the sensor glucose readings, trend graphs, trend arrows and alerts you when your glucose is too high or too low or if there is something you should be aware of or need to do. The receiver is neither water resistant nor waterproof and can get damaged if moisture gets inside, so keep it away from any liquids and very high humidity.

#### Adverse Effects / Risks.

Inserting the sensor and wearing the adhesive patch might cause infection, bleeding, pain or skin irritations (redness, swelling, bruising, itching, scarring or skin discoloration). There is a low chance of this happening. In the clinical study for the Dexcom G4 PLATINUM System, only slight redness and swelling occurred in a few patients. If any of these events happen, the patient might feel discomfort in the area the sensor is inserted. There is a remote chance that a sensor fragment could remain under your skin if the sensor breaks while patient is wearing it. This did not happen in the clinical study for the Dexcom G4 PLATINUM System. If you think thinks a sensor has broken under your skin, he shall contact contact the study personnel and call Dexcom's Technical Support. Sensor breakage may cause some anxiety, but it is not a significant medical risk.

#### Contraindications.

The Dexcom sensor, transmitter, and receiver must be removed before Magnetic

CONFIDENTIAL

This material is the property of the NYU School of Medicine and Langone Medical Center. Do not disclose or use except as authorized in writing by the study sponsor

Use of continuous glucose monitoring system with intensive feedback in adolescents with poorly controlled type 1 diabetes  
Version Date: 04/26/2018

Resonance Imaging (MRI), Computed Tomography (CT) scan, or diathermy treatment. The device is MR Unsafe. The magnetic fields and heat could damage the device so that it might not display sensor glucose readings or provide alerts, and patients might miss a low or high blood glucose value.

Taking medications with acetaminophen (such as Tylenol) while wearing the sensor may falsely raise the sensor glucose readings. The level of inaccuracy depends on the amount of acetaminophen active in the body and may be different for each person.

